**Population Level Summary:**

For participants randomized to WL/NIR-F, the score of the ureter conspicuity at the 30-min time point based on the 5-Point Likert Scale with NIR-F will be compared with the score of the ureter conspicuity at the 30-min time point based on the 5-Point Likert Scale with WL using absolute difference.

## 4 STUDY DESIGN AND DOSE RATIONALE

### 4.1 Overall Study Design

This is a phase 3, multicenter, prospective, randomized, open-label study to evaluate the clinical utility of ASP5354 with the use of an NIR-F imaging device in participants undergoing minimally invasive and open abdominopelvic surgeries. In order to achieve reasonably balanced enrollment across surgery types the sponsor will monitor enrollment and may cap enrollment for a specific surgery type (i.e., gynecological or other abdominopelvic) during the study. This study will be conducted in approximately 6 clinical sites in the US.

This study is designed to evaluate the clinical utility of ASP5354 which enhances the conspicuity of the ureter with the use of an NIR-F imaging device. The investigator, at their discretion, will select ureter(s) of interest (i.e., right, left, or both) before surgery. If the selection is both, the investigator will further select 1 index ureter (i.e., right or left) at their discretion. The conspicuity of the ureter will be assessed by the investigator (5-Point Likert Scale) for the selected ureter(s) of interest during surgery for all participants. The investigator's qualitative assessment of ureter conspicuity will be supported with a quantitative measure and a BICR assessment, which will be performed centrally using recorded images taken during the surgery.

The study will enroll approximately 107 participants (84 adults with normal renal function or mild renal impairment [eGFR  $\geq$  60 mL/min], up to 10 adults with moderate or severe renal impairment [eGFR  $\geq$  15 to < 60 mL/min] and 13 adolescents with normal renal function or mild renal impairment [eGFR  $\geq$  60 mL/min]) who will receive a single intravenous 3 mg dose of ASP5354. The normal/mild eGFR cohort will be randomized to 2 arms: WL/NIR-F and WL-only. Randomization will be stratified by type of surgery (gynecological; other abdominopelvic). There is no randomization for adult participants in the moderate/severe eGFR cohort or adolescent participants, and all of these participants will be evaluated with WL/NIR-F. Safety, tolerability and pharmacokinetics in the study population will also be assessed.

For additional details on each cohort, please refer to [Sections 7.1.2, 7.1.3 and 7.1.4] for adults with normal/mild eGFR, adults with moderate/severe eGFR and adolescents, respectively.

### 4.2 Scientific Rationale for Study Design

There are currently no approved imaging agents for ureter identification during open or minimally invasive abdominopelvic/pelvic surgeries. A multicenter, prospective, randomized and open-label study design was chosen to evaluate the intraoperative ureter conspicuity using NIR-F by the operating investigator after administration of ASP5354 compared with ureter conspicuity by WL within each study participant in the WL/NIR-F arm. To reduce the investigator's bias, the WL-only arm is added to cast doubt in the investigator's mind as to whether NIR-F illumination mode will be used for a given participant, which may enhance more consistent behavior (similar due diligence) for evaluation with WL versus NIR-F. Conspicuity assessments in the WL/NIR-F arm will be completed throughout surgery to

evaluate the clinical utility of ASP5354 in ureter visualization. In the WL/NIR-F arm, the first assessment will always be under WL followed by NIR-F assessment. Additionally, a confirmatory blinded independent central review (BICR) will be employed to independently read all WL and NIR-F images for all timepoints for all participants in the WL/NIR-F arm.

ASP5354 has been studied in 2 phase 1 studies in healthy participants and in 1 phase 2 study in participants undergoing laparoscopic or minimally invasive colorectal surgery. ASP5354 was shown to be safe and well tolerated at a single intravenous dose up to 24 mg in the US phase 1 safety and pharmacokinetic study in healthy participants (5354-CL-0001). No treatment-related serious or non-serious AEs were reported in this study. The Japanese phase 1 study (5354-CL-0002) findings are consistent with those observed in the US phase 1 study. No safety issues were reported with no clinically significant changes in vital signs, 12-lead electrocardiogram (ECG), clinical laboratory evaluation or physical examination.

ASP5354 has also been studied in a phase 1 study in participants with mild, moderate or severe renal impairment compared with healthy controls at a 3 mg dose:

- No significant safety findings have been identified from clinical trial 5354-CL-0004 (A phase 1, open-label study to evaluate the pharmacokinetics, safety and tolerability of ASP5354 in participants with renal impairment compared to healthy participants with normal renal function). The safety data included a total of 7 non-serious treatment-emergent adverse events (TEAEs) that were reported of the 28 participants enrolled. The TEAEs were single occurrences and included: anemia aggravated, sore throat, headache, flatulence, bloating, diarrhea and hyperbilirubinemia.
- Only 2 of the non-serious TEAEs (headache grade 1 and hyperbilirubinemia grade 1) were considered related to ASP5354, which occurred in healthy participants with normal renal function:
  - The headache occurred on day 1 (day of ASP5354 administration) and resolved on day 3, as judged by the investigator.
  - The hyperbilirubinemia occurred on day 8 and resolved on day 14, as judged by the investigator.

The inclusion of adolescents in a phase 3 study was proposed because ASP5354 has shown an acceptable safety and tolerability profile similar to ICG. Pharmacokinetic modeling and simulation has suggested that systemic exposure ( $C_{max}$  and  $AUC_{inf}$ ) in adolescents (12 to < 18 years of age) is comparable to those in adults ( $\geq 18$  years of age). Also, it is expected that adolescent participants will have similar efficacy/visualization when they have similar exposures of ASP5354 as adults.

#### **4.2.1 Participant Input into Study Design**

[figure not shown]
There was no participant involvement in the design of the study.

#### **4.3 Dose Rationale**

The dose selection for the phase 3 studies was based on data from the phase 2 dose-ranging study (5354-CL-0201) conducted in adult participants undergoing laparoscopic/minimally

invasive colorectal surgery. Single intravenous doses of ASP5354 (pudexacianinium chloride) 0.3, 1 and 3 mg were administered. ASP5354 was safe and well tolerated when administered as single intravenous ascending doses up to 3 mg. Doses of 1 mg and 3 mg provided visualization throughout the duration of the surgical procedure; however, at the 3 mg dose, fluorescent intensity was stronger and more consistent. At the 1 mg dose, the intensity of fluorescence was variable [Figure 1] amongst the participants evaluated in the phase 2 study. The lower dose (0.3 mg) was determined to be inadequate for ureter visualization due to lower fluorescence intensity and shorter duration of visualization than doses of 1 mg and 3 mg. Given the ASP5354 safety profile described in [Section 4.2], the highest dose of 3 mg was selected for the phase 3 program to provide optimal conspicuity of the ureter for the duration of surgery in all intended participants for the phase 3 clinical program, including renally impaired participants.

[figure not shown]
**Figure 1**    **Fluorescence Intensity of the Index Ureter at Each Time Point During Surgery**

Source: [Albert et al, 2023]

Using the PopPK model, plasma concentration data from the phase 2 study was used to predict urine ASP5354 concentration data. The relationship between simulated urine concentrations and the intensity of fluorescence from the Likert scale was evaluated for the 0.3, 1, and 3 mg doses. The 3 mg dose showed consistent efficacy with regards to intensity of fluorescence and was above the target urinary concentration for ureter visualization of 1  $\mu$ g/mL, which was determined based on nonclinical ex vivo and in vivo minipig studies [Fushiki et al, 2023] [Figure 2]. In contrast, the 1 mg dose did not show consistency across the Likert scale regarding intensity of fluorescence and also depicted a high amount of variability even though it was above the target urinary concentration for ureter visualization of 1  $\mu$ g/mL. Therefore, the 3 mg dose was selected for the phase 3 program.

**Figure 2 Predicted Urine Pudexacianinium Concentration Data Versus the Intensity of Fluorescence (e.g., Likert Scale) From the Phase 2 Study**

Source: [5354-PK-0005 PKPD report]

## 4.4 Start and End of Study Definitions

### *First act of recruitment*

The study start date is the date on which the clinical study will be open for recruitment of participants.

The first act of recruitment is the date the first participant signs the informed consent form (ICF) and will be the study start date.

### *End of study*

The end of the study is defined as the last visit or assessment shown in Schedule of Assessments [Table 1] for the last participant in the study.

A participant is considered to have completed the study if the participant has completed all periods of the study including the last assessment shown in the schedule of assessments.

## 5 STUDY POPULATION

All screening assessments must be completed and reviewed to confirm the potential participant meets all eligibility criteria. Prospective approval of protocol deviations to eligibility criteria (also known as protocol waivers or exemptions) is not permitted.

### 5.1 Inclusion Criteria

Participant is eligible for participation in the study if all of the following apply:

1. Institutional Review Board (IRB)/Independent Ethics Committee (IEC) approved written informed consent and privacy language as per national regulations (e.g., Health Insurance Portability and Accountability Act [HIPAA] authorization for US study sites) must be obtained from the participant or participant's parent or legal guardian, and if required, assent from adolescent participant ( $\geq 12$  to  $< 18$  years of age) prior to any study-related procedures (including withdrawal of prohibited medication, if applicable).
2. Participant is  $\geq 12$  years of age at the time of signing an ICF.
3. Participant is scheduled to undergo minimally invasive or open abdominopelvic surgery that may require ureter identification.
4. Participant has normal renal function or has varying degrees of chronic kidney disease as defined by the National Kidney Foundation and calculated by individual eGFR using the modification of diet in renal disease (MDRD) formula for adults or the Schwartz formula for adolescents at the screening visit (see [Section 10.7]).
  - Adult normal/mild eGFR cohort: eGFR  $\geq 60$  mL/min
  - Adult moderate/severe eGFR cohort: eGFR  $\geq 15$  to  $< 60$  mL/min
  - Adolescent cohort: eGFR  $\geq 60$  mL/min
5. Female participant is not pregnant (see [Section 10.2]) and at least 1 of the following conditions apply:
  - a. Not a woman of childbearing potential (WOCBP; see [Section 10.2])
  - b. WOCBP who agrees to follow the contraceptive guidance (see [Section 10.2]) from the time of informed consent through at least 30 days after study intervention administration.

6. Female participant must agree not to breastfeed starting at the administration of ASP5354 through 30 days after ASP5354 administration.
7. Female participant must not donate ova starting at the administration of ASP5354 through 30 days after ASP5354 administration.
8. Male participant with female partner(s) of childbearing potential (including breastfeeding partner) must agree to use contraception (see [Section 10.2]) through at least 30 days after ASP5354 administration.
9. Male participant must not donate sperm starting at the administration of ASP5354 through 30 days after ASP5354 administration.
10. Male participant with pregnant partner(s) must agree to remain abstinent or use a condom for the duration of the pregnancy from the start of ASP5354 administration through 30 days after ASP5354 administration.
11. Participant (and/or participant's parent or legal guardian) agrees not to participate in another interventional study involving unapproved study medications while participating in the present study.

## **5.2 Exclusion Criteria**

Participant will be excluded from participation in the study if any of the following apply:

1. Participant has any physical or psychiatric condition, which, in the investigator's opinion, makes the participant unsuitable for study participation.
2. Participant is anticipated to require ureteral stenting during surgery.
3. Participant has an active urinary tract infection requiring antibiotic therapy.
4. Participant has moderate to severe cardiac disease that limits daily functioning (New York Heart Association Class III to IV) or other medical conditions that the investigator feels would impact safety or study compliance.
5. Participant has any clinically relevant laboratory abnormality that could contraindicate surgery in the opinion of the investigator.
6. Participant with body weight < 30 kg.
7. Participant has a known or suspected hypersensitivity to ASP5354, ICG or any components of the formulation used.
8. Participant has had previous exposure to ASP5354.
9. Participant has been administered ICG or other NIR-F imaging agents within 48-hours prior to ASP5354 administration, with the exception of participants who receive ICG for lymphatic mapping before the surgery.
10. Participant has received any investigational therapy within 28 days or 5 half-lives, whichever is longer, prior to randomization.
11. Participant is on hemodialysis, hemodiafiltration or peritoneal dialysis

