**Intercurrent Events (ICEs) and Strategies:**

*ICE1:* Participants who have received the medications or therapy listed below within 48 hours prior to ASP5354 administration and/or before the completion of the surgical procedure:

- ICG, unless used for anastomotic evaluation after the ureters have been visualized or for lymphatic mapping where there is a clear anatomic separation of the ureters and the lymphatics
- Other NIR-F imaging agents
- Ureteral stent

*Composite strategy for ICE1:* The assessment of ureter conspicuity after ICE1 will not be considered as relevant and will be handled as missing data. For participants that experience ICE1 prior to the 30-min time point conspicuity assessment by the investigator, both conspicuity values at the 30-min time point with WL and NIR-F will be set as '1 = Not self-evident' for the primary endpoint analysis.

*ICE2:* Participants who are unable to have ureter conspicuity assessed by the investigator at the 30-min time point for any reason.

*Treatment policy strategy for ICE2:* The assessment of ureter conspicuity in the event of ICE2 will be imputed as follows. In the event that WL or NIR-F conspicuity is not assessed by the investigator at the 30-min time point, the first collected conspicuity assessment under the respective illumination mode will be used as the 30-min time point value. If a participant does not have any assessments under a respective illumination mode during the entire surgery, the 30-min time point value will be set as the 30-min value from the other illumination mode. If a participant does not have any assessments under either illumination mode during the entire surgery, both 30-min time point values will be set as '1 = Not self-evident'.

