## 6.8 Prior and Concomitant Therapy

The following concomitant medications listed below will not be allowed within 48 hours prior to ASP5354 administration through the completion of the surgical procedure:

- ICG unless used for anastomotic evaluation after the ureters have been visualized or for lymphatic mapping where there is a clear anatomic separation of the ureters and the lymphatics
- Other NIR-F imaging agents

Participants anticipated to require ureteral stents during surgery are excluded from the study [Exclusion Criterion No.2]. Ureteral stents however may be used based on clinical judgment of the investigator during surgery. Diuretics should be avoided 48-hours prior to ASP5354 administration until the completion of the surgical procedure but can be used based on clinical judgment of the anesthesiologist or investigator.

A list of excluded concomitant medications is provided in [Section 10.5].

Concomitant and corrective treatments (medication and non-medication therapy) will be recorded in the eCRF. However, there is no need to record supplements, nutrients or intravenous solutions for hydration.

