### **9.3.2 Primary Endpoint/Estimand(s) Analysis**

#### **9.3.2.1 Primary Analysis**

The primary efficacy endpoint is the investigator's blinded assessment of the intra-participant difference in ureter conspicuity for WL versus NIR-F at the 30-min time point after ASP5354 administration based on a 5-Point Likert scale. The population used for the primary efficacy analysis will be the ITT population, which includes all participants in the adult normal/mild eGFR cohort randomized to the WL/NIR-F arm. Adolescents and moderate/severe renally impaired participants that are enrolled directly into the WL/NIR-F arm will not be included in the primary analysis. The primary endpoint will be analyzed using a paired t-test.

Prior to the analysis, data will first be imputed as follows if participants experience either ICE1 or ICE2 (refer to primary estimands in [Section 3.1]):

- Participants who experience ICE1 will have both their NIR-F and WL conspicuity assessments at the 30-min time point after ASP5354 administration imputed as '1 = Not self-evident' for the primary endpoint analysis.
- Participants who experience ICE2 and do not have either a NIR-F or WL conspicuity assessment conducted at the 30-min time point after ASP5354 administration will have the first collected conspicuity assessment under the respective illumination mode used as

the 30-min time point value. If a participant does not have any assessments under a respective illumination mode during the entire surgery, the 30-min time point value will be set as the 30-min value from the other illumination mode. If a participant does not have any assessments under either illumination mode during the entire surgery, both 30-min time point values will be set as '1 = Not self-evident'.

Descriptive statistics will be used to summarize the ureter(s) conspicuity at the 30-min time point after ASP5354 administration with WL and the 30-min time point with NIR-F.

Descriptive statistics for the differences between the ureter(s) conspicuity scores and 95% 2-sided confidence interval for the mean difference and P value will be presented.

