### **9.3.2.2 Sensitivity Analysis**

A sensitivity analysis for the primary endpoint will be conducted. The same paired t-test as the primary analysis will be run with the assessments impacted by ICE1 or ICE2 left as missing.

An additional sensitivity analysis for the primary endpoint will be conducted. The NIR-F and WL conspicuity assessments at the 30-min time point after ASP5354 administration will be compared using a Wilcoxon signed-rank test. This analysis will be conducted using the same data (with ICE1 and ICE2 imputation) as the primary analysis.

Sensitivity analyses will be conducted on the ITT population.

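### Exclusion 9 exempts all ICG lymphatic mapping before surgery, while Section 6.8, Appendix 5 and ICE1 exempt it only conditionally, so an eligible participant could enter ITT with the primary difference already fixed at 0

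*Protocol*

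**What the plan says.** - **Eligibility (Protocol 5.2, Exclusion 9).** The base rule excludes a candidate when "Participant has been administered ICG or other NIR-F imaging agents within 48-hours prior to ASP5354 administration". The exemption is "with the exception of participants who receive ICG for lymphatic mapping before the surgery". It carries no anatomical condition and does not refer to Section 6.8 or 10.5.
- **Prohibited medication (Protocol 6.8, repeated in 10.5, footnote 1).** ICG and other NIR-F agents "will not be allowed within 48 hours prior to ASP5354 administration through the completion of the surgical procedure". One exemption is for anastomotic evaluation once the ureters have been seen. The other is "for lymphatic mapping where there is a clear anatomic separation of the ureters and the lymphatics".
- **Estimand (Protocol synopsis and 3.1; SAP 5.1).** ICE1 is receipt of these agents "within 48 hours prior to ASP5354 administration and/or before the completion of the surgical procedure", with the same two exemptions as Section 6.8.
- **Handling.** When ICE1 precedes the 30-minute assessment, "both conspicuity values at the 30-min time point with WL and NIR-F will be set as" 1. Protocol 9.3.2.1 and SAP 6.4.1.1 repeat this for the primary analysis.
- **Analysis set (Protocol 9.2; SAP 4.1).** ITT is every adult in the normal/mild eGFR cohort randomised to WL/NIR-F. ICE1 does not remove anyone from it.

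**The concern.** Three parts of the plan classify the same exposure over the same 48 hours before dosing, and they do not agree. Mapping without clear separation of ureters and lymphatics is admitted by the eligibility rule, forbidden by the medication rule, and scored as a failure by the estimand.

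A participant can then be enrolled in line with Section 5.2 although the primary outcome is settled before the surgeon looks. The result says nothing about ASP5354; it follows from the imputation rule alone. What is at stake is the size of the estimated effect, some power, and whether sites and data managers can classify such a case the same way.

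**Working it through.** **1. One exposure under each rule.** Take ICG given for lymphatic mapping before surgery, within 48 hours before dosing, in an adult of the normal/mild eGFR cohort.

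| Rule | Clear separation | No clear separation |
|---|---|---|
| Exclusion 9 | eligible | eligible |
| 6.8 and 10.5 | allowed | prohibited |
| ICE1 (Protocol 3.1, SAP 5.1) | not an event | event before the 30-minute assessment |

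The conflict is confined to the right-hand column. The other exemption in 6.8, 10.5 and ICE1 (anastomotic evaluation after the ureters are seen) does not cover mapping ICG given before dosing.

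**2. What the imputation then gives in the WL/NIR-F arm.**

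- H1 (30 minutes): NIR-F minus WL = 1 − 1 = 0.
- H2 (mean of NIR-F time points): Protocol 9.3.3.1 and SAP 6.4.2 set NIR-F scores after ICE1 to the 30-minute WL value, here 1. Every difference is 0, so the mean is 0. A zero has no sign, and neither document says how the sign test treats it.
- H3 (end of surgery): the same imputation applies, so the difference is 0.

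**3. The plan's own sample size.** Inputs from Protocol 9.5.1.1: difference 1.0, common SD 2.0, correlation 0.2, two-sided 0.05, 90% power, 84 randomised.

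- Variance of the paired difference = 2 × 2.0² × (1 − 0.2) = 6.4, so SD = 2.530.
- Normal approximation: n = (1.960 + 1.282)² × 6.4 / 1.0² = 67.2, so 68.
- Exact paired t-test (noncentral t): n = 70, power 90.3%.

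The allocation ratio is left to a separate document. An arm of 70 would follow from 5:1 (84 × 5/6 = 70). I use 70 as an assumption.

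**4. Effect of preset zeros on H1.** Let k of 70 be set to 0, f = k/70, and let the rest follow the design assumption. Then mean = 1 − f and variance = (1 − f) × 6.4 + f × (1 − f). For k = 3: f = 0.0429, mean = 0.957, variance = 6.167, SD = 2.483.

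| k of 70 | Mean difference | Power |
|---|---|---|
| 0 | 1.00 | 90.3% |
| 1 | 0.99 | 89.9% |
| 3 | 0.96 | 88.9% |
| 5 | 0.93 | 87.8% |
| 7 | 0.90 | 86.6% |
| 14 | 0.80 | 81.9% |

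With 63 in the arm (3:1), power is 87.0% with no zeros and 82.3% with 7.

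**5. Comparison with leaving them missing.** Dropping 3 of 70 gives 89.0% power and dropping 7 gives 87.0%, against 88.9% and 86.6% when they are set to 0. Most of the power loss is therefore loss of usable participants. The shrinkage of the estimate (to 0.96 or 0.90) comes from the zeros themselves.

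**The case against.** The strongest reply is that the rules stack. Section 6.8 binds the same site as Section 5.2, Appendix 5 tells investigators to check for prohibited drugs, and waivers are not allowed. A site that obeys the stricter rule never reaches the preset zero. This is right as far as it goes: the zero requires a breach of Section 6.8. It does not remove the conflict, because no eligibility criterion asks about separation before randomisation, and a breach of 6.8 does not take the participant out of ITT.

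A second reply is that eligible participants who meet ICE1 are foreseen. Unplanned ureteral stents are handled that way. But for stents the exclusion and ICE1 point the same way: anticipated stenting is excluded, and only later use becomes an event. For mapping, the exclusion criterion expressly lets the exposure in.

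A third reply stands in part. Randomisation may take place one business day before surgery, and dosing is intraoperative. ICG given after eligibility is settled cannot be screened out and is left to 6.8 and ICE1.

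Three stronger readings are tempting and are not supported:

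- **That such participants will be enrolled.** The documents give no count or rate, so this remains a possibility.
- **That the problem falls mainly in one surgery-type stratum.** No section links ICG mapping to gynaecological or other abdominopelvic surgery.
- **That unrecorded ICG will contaminate NIR-F scores.** Protocol 2.1 does describe the two agents as optically alike. But concomitant treatments are recorded (Protocol 6.8), excluded medication is a named deviation class (SAP 6.2.2), and ICEs are tabulated with a separate ICG line and listed (SAP 6.4.5). Failure to record would be a breach of the plan, not a consequence of it.

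**Conclusion.** The conflict is real and sits in current text. It needs no figure to establish it. Its reach is limited: only ITT participants affect H1 to H3. WL-only participants are outside these analyses, and the adolescent and moderate/severe cohorts are affected only in descriptive summaries.

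The size is unknown because the frequency is unknown. Under the design assumptions and an assumed arm of 70, three cases cost 1.4 percentage points of power (90.3% to 88.9%) and seven cost 3.7 (to 86.6%). The assumed difference of 1.0 falls to 0.96 and 0.90.

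A reader might infer that the primary test is invalid. It is not: the zeros pull the estimate towards no difference and do not inflate false positives. The sensitivity analysis run "with the assessments impacted by ICE1 or ICE2 left as missing" shows the result without them, though it removes ICE2 cases as well and so does not isolate this route. The point is a moderate one, worth correcting because the correction is cheap.

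**What to change.** Reconcile Exclusion 9 with Protocol 6.8, 10.5 and ICE1 (Protocol synopsis and 3.1, SAP 5.1), so that the same ICG-mapping exposure has one classification for eligibility, for prohibited medication and for the estimand. Apply that classification before randomisation or registration where the exposure is known by then, and leave later exposure to 6.8 and ICE1. Which clinical condition should stand is for the sponsor to decide; the statistical requirement is only that the sections agree.

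The cost is about one clause of protocol text, with a matching SAP edit if the ICE1 wording changes. Depending on the condition chosen, some candidates may become screen failures, or some exposures may cease to count as ICE1. No change to the test, the analysis sets or the sample size is needed.
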